3.4.2 Exclusion Criteria

Patients who are enrolled in a clinical trial for other TPO receptor agonists (eg, clinical trials for eltrombopag) will be excluded from the study.

Patients are excluded from the cohorts of chronic ITP patients if either of the following is present:

1. Any diagnosis of another condition associated with thrombocytopenia other than chronic ITP listed in [Appendix 2](#) at any time prior to or within 6 months after the qualifying diagnosis for chronic ITP. Examples of thrombocytopenia associated with other diseases and conditions include systemic lupus erythematosus (SLE), HIV infection, hepatitis C virus infection, malignancy, lymphoproliferative disorders, and myelodysplastic syndrome.
2. Lack of a platelet count below $150 \times 10^9/L$ without obvious cause in the 6 months before or after their first ITP diagnosis code

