Because ITP is a diagnosis of exclusion and secondary causes of thrombocytopenia may be difficult to diagnose, some patients will require review of NHRS databases, medical records (electronic and/or paper charts), and laboratory data including bone marrow exams, if any, prior to their first diagnosis of ITP. These will include the relevant time periods prior to their first diagnosis of ITP for all patients who have a history of other primary thrombocytopenia (D69.4) or any condition from [Appendix 2](#) prior to the first diagnosis of ITP.

Cases with either increased BM reticulin or BM fibrosis (with/without associated clinical signs) and hematological malignancies (AML and MDS) will be ascertained using electronic medical record review. Confirmation of the diagnosis of BM reticulin/collagen fibrosis or AML/MDS will be accomplished by evaluation of the results of BM biopsies.

Selected data fields of each adult chronic ITP patient (prevalent cases as of 01 January 2009 and incident cases thereafter) and of patients who receive romiplostim therapy during the study period, will be extracted and analyzed to evaluate the endpoints listed in [Section 6.2](#). These selected data fields include those for the patient population using other thrombopoietic agents, since these agents could have a confounding impact on the occurrence of study outcomes such as BM fibrosis. In addition, the study will last up to 11 years and it will include both prevalent cases between 1996 and 2008 and incident cases from 2009 through 2018. The diagnoses, treatment procedures, medication, and practice patterns may be significantly changed; therefore, the study will use an inception cohort approach to define the study cohort based upon year of initial ITP diagnosis. Dependent upon sample size, the inception cohorts can be established as from 1996 to 2000, 2001 to 2005, 2006 to 2010, 2011 to 2015, and 2016 to 2018.

Patients and incidence rate of study outcomes will be compared among these inception cohorts.

To describe the romiplostim off-label utilization pattern, the study will also include patients without an adult chronic ITP diagnosis, but who are exposed to romiplostim. An example would be the inclusion of patients diagnosed with pediatric ITP, MDS, HIV/AIDS diagnoses, and who have received romiplostim therapy. Patients exposed to romiplostim with off-label use will be directly identified by drug codes for romiplostim as the codes are adopted in each participating country.

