3.4 Selection of Participants (or Subject Eligibility)

3.4.1 Inclusion Criteria

Subjects in the NCPRR will be those whose health information is recorded by the NHRS of Denmark, Norway, or Sweden.

The eligible adult cITP romiplostim-exposed patients for the NCPRR must meet all of the following criteria:

- Patients must be 18 years or older at the time of chronic ITP diagnosis,
- Patients will have romiplostim therapy between 01 January 2009 and 31 December 2018, and
- Patients will have at least 6 months of medical information prior to initial date of receiving romiplostim treatment (Index Date), data from which will establish a baseline of study subjects.

The eligible adult cITP romiplostim-unexposed patients for the NCPRR must meet all following criteria:

- Patients must be 18 years or older at the time of chronic ITP diagnosis,
- Patients will not have received romiplostim therapy prior to or during the study period between 01 January 2009 and 31 December 2019, and
- Patients will have at least 6 months of medical information in the study period. The data from this period will establish baseline of subjects in the comparison group.

Eligible romiplostim-unexposed cITP patients will be the source of comparison cohorts for romiplostim-exposed cITP patients. Because potential confounding factors (eg, severity of ITP condition) may cause some biases for the study, however, robust propensity scoring and adjusted analyses will be essential ([Section 12](#)). In addition, appropriate contextualization from other recognized data sources will be used in comparisons to address selection biases.

In addition, according to initial dates of receiving romiplostim therapy among patients in the Exposed Cohort, the follow-up time period will be separated into 2 periods: (1) follow-up time period prior to romiplostim exposure, and (2) follow-up time period following romiplostim exposure. Patient experiences in the follow-up time period prior to the initial date of receiving romiplostim therapy will be considered as another “within-patient” comparison with the patient experiences during the follow-up time period after the initial date of receiving romiplostim therapy.

Eligible romiplostim Off-Label-Exposed patients will be any patient who received romiplostim therapy without an adult chronic ITP diagnosis.

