6. DEFINITION OF EXPOSURE, OUTCOME, AND OTHER STUDY VARIABLES

6.1 Exposure

Exposure is defined as the patient receiving romiplostim therapy.

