6.3 Other Study Variables – Predictors and Independent Variables

There are many potential predictors for the effectiveness and safety of romiplostim. To further describe the effects of romiplostim therapy, the study will consider the following variables in study cohort establishment and analysis:

Variables considered in study cohort and patient strata establishment will include:

- Sex
- Age
- Race/ethnicity
- Body Mass Index (BMI) and/or Body Surface Index (BSI)
- Year of initial ITP diagnosis (1996 to 2000, 2001 to 2005, 2006 to 2010, 2010 to 2015, and 2016 to 2018)

- Country (the study will be conducted based upon the NHRS from each country, independent of the country considered)
- Adult chronic ITP disease condition: There are many factors that may affect the adult chronic ITP disease condition (eg, length of disease, severity, platelet counts, splenectomy, co-morbidity, and concurrent medication); therefore, a propensity score will be developed to establish the romiplostim Exposed Cohort and Unexposed Cohort for adult chronic ITP patients. The development of a propensity score is discussed in [Section 12.3](#).

Key variables considered in the analysis

- Demographic characteristics (eg, age and sex)
- BMI and/or BSI
- Disease conditions (eg, length of disease, severity, platelet counts, surgical procedure received, splenectomy, etc.)
- Propensity score (will be separated into 5 strata)
- Concurrent medication (eg, thrombopoietic agents)
- Surgical procedures (eg, splenectomy)
- Comorbidities (eg, infections, diabetes and disease or conditions that increase risk of thrombotic event)
- Medication durations and dosage

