7.3 Time at Risk

Time at risk for the NCPRR is defined as from time after initial romiplostim exposure to occurrence of outcomes listed in [Section 6.2](#). For patients without these study outcomes, the time at risk will be from the index date to death, loss to follow-up, or the end of study, whichever comes first.

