12.4 Analysis for Long-term Effects

Analysis for long-term effects will be descriptive in nature. As the selection bias resulting from confounding by indication for this study could be very large, and as some impacts are not measurable, comparative analyses will be inherently challenging to interpret. For these reasons any comparative analyses must be considered as exploratory for signal detection and for the purpose of hypothesis generation. The incidence rates of clinically significant bleeding (inpatient and outpatient) and/or rescue medication use will be described for the Exposed Cohort and Unexposed Cohort:

- Kaplan-Meier survival curves will be constructed for patients with bleeding events for the Exposed Cohort and Unexposed Cohort.
- As needed, a Cox model with romiplostim exposure as a time-varying covariate will be used to compare the total event-free survival rates among exposed ITP patients and the unexposed cohort, with an estimation of the relative risk and associated 95% confidence interval. This analysis will adjust for potential confounders and propensity scores. Stratification by propensity score, significant year spans, and country may be considered for this analysis, although such an analysis will only be for exploratory and hypothesis generating purposes. Other treatment exposures,

health status, and disease conditions may also be considered for inclusion in the model as time-varying covariates.

Comparison of platelet counts in predefined time periods (prior to, during, immediately after treatment cessation, and post treatment) between the Exposed Cohort and Unexposed Cohort:

- Mean and SD
- As needed, a multiple regression will be used to test the difference between the Exposed Cohort and Unexposed Cohort. However, such an analysis will only be for exploratory and hypothesis-generating purposes.

Comparison of long-term safety (eg, thromboembolic risk, thrombocytosis, hematological malignancies, focused upon AML, and MDS), including:

- Description of rare and long latency events: Some events (eg, AML and MDS) are too few to conduct any meaningful statistical analysis or comparison. The study will provide detailed case descriptions for each case observed.
- Incidence rate of these events will be calculated.

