12.6 Comparisons of Outcomes that are Dependent on BM Data

1) Frequency and incidence of increased BM reticulin and/or BM fibrosis with associated clinical signs⁵, confirmed by findings in a BM biopsy and 2) frequency and incidence of collagen fibrosis with associated clinical signs confirmed by findings in BM biopsies will be analyzed between the Exposed Cohort and Unexposed Cohort in all adults with chronic ITP:

⁵ Clinical signs: any of the following: splenomegaly, hepatomegaly, leukocytosis, and cytopenia.

- Since the sample size could be very small, the detailed description of each identified case will be listed in the report.
- If there is a sufficient sample size, a formal statistical analytic comparison, as described in [Section 12.4](#), will be conducted.

Description of prevalence rate of reticulin and collagen formation among chronic ITP patients:

- This analysis will be conducted based upon all eligible adult chronic ITP patients in the period prior to romiplostim treatment by splenectomy status. Only initial BM results will be used in the analysis to reduce potential selection bias caused by repeated testing for BM with abnormal findings.
- Prevalence of patients with reticulin and collagen formation in BM will be assessed. No comparison will be conducted; however, the descriptive analysis will be used to describe demographic characteristics, clinical features, and laboratory findings.

1) Frequency and incidence of chronic idiopathic myelofibrosis (primary myelofibrosis) according to the WHO diagnostic criteria, and 2) overall and specific incidence rates of BM fibrosis findings, including reticulin and collagen fiber content formation, and chronic idiopathic myelofibrosis in the Exposed Cohort and Unexposed Cohort in adult chronic ITP patients who have BM data prior to and post romiplostim therapy:

- Since the sample size could be very small for these outcomes, the detailed description of each identified case will be listed in the report.
- If there is a sufficient sample size (e.g., approximately 10 per treatment group for each covariate considered), a formal statistical analytic comparison, as described in [Section 12.4](#), will be conducted.

2) Association of splenomegaly and/or hepatomegaly with BM fibrosis and 2) association of changes in peripheral blood prior to and following the finding of reticulin and collagen fiber content or formation (reticulin grading 1 to 3):

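### Prescribed use of other TPO receptor agonists is neither excluded nor separated, so the crude cohort incidence rates mix it with unexposed and romiplostim-exposed time

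*Protocol*

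**What the plan says.** Four protocol definitions decide where person-time on another TPO receptor agonist goes.

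- Section 3.4.2 removes trial participants only: "Patients who are enrolled in a clinical trial for other TPO receptor agonists (eg, clinical trials for eltrombopag) will be excluded from the study".
- Section 3.4.1 bars romiplostim, and nothing else of the class, from the unexposed cohort: "Patients will not have received romiplostim therapy prior to or during the study period between 01 January 2009 and 31 December 2019".
- Section 6.1: "Exposure is defined as the patient receiving romiplostim therapy".
- Section 7.3, for patients without an outcome: "the time at risk will be from the index date to death, loss to follow-up, or the end of study, whichever comes first". Section 3.6 agrees.

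The protocol is aware of the class. Section 2.3 describes increased reticulin as an expected, on-target consequence of TPO stimulation. Section 3.1 extracts data on users of other thrombopoietic agents "since these agents could have a confounding impact on the occurrence of study outcomes such as BM fibrosis". Section 6.3 lists thrombopoietic agents, under concurrent medication, among the key analysis variables. Section 12.4 says of other treatment exposures, together with health status and disease, only that they may enter the Cox model as time-varying covariates: "health status, and disease conditions may also be considered for inclusion in the model".

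**The concern.** A patient who takes another prescribed TPO receptor agonist and never romiplostim is plain unexposed time. One who takes such an agent first and romiplostim later contributes the earlier period to the unexposed cohort under section 3.1. One who moves from romiplostim to another agent stays in exposed follow-up to the end of study. No rule excludes, censors or separately reports any of this time.

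The outputs that are certain to appear are the annual and cumulative incidence rates by cohort (section 12.2), and these carry the mixture. For the unexposed cohort the question is dilution: class users may raise the comparator's rate of the marrow outcomes under study. For the exposed cohort it is attribution: an event arising on another agent after a switch enters the rate in romiplostim recipients, which is the primary objective. Calling the comparisons exploratory does not address the second.

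**Working it through.** **1. Does the stated handling separate the rates?**

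- The section 6.3 variable works through a model. The time-varying form is optional, and for the marrow outcomes section 12.6 warns of very small numbers and makes modelling conditional: "If there is a sufficient sample size, a formal statistical analytic comparison".
- The propensity score (section 12.3) uses the six months before the index date, so it cannot see later starts or switches.
- Narratives of marrow fibrosis cases show other agents taken by the cases. They give no person-time denominator.
- The section 7.1 periods distinguish time on romiplostim from time after it. They do not distinguish time after it on another agent from time on none, and they do nothing for the unexposed cohort.

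**2. The plan's own power figure.** Inputs from section 11: 4,234 exposed and 12,700 unexposed patient-years. The protocol gives no alpha for Appendix 1, so two-sided 0.05 is assumed. Under an exact conditional test of two Poisson rates, the exposed share of events is 4,234/(4,234 + 12,700) = 0.25 if there is no effect. At background 0.5% and RR 2, expected events are 0.005 × 2 × 4,234 = 42.3 exposed and 0.005 × 12,700 = 63.5 unexposed. Power is 89.6%; Appendix 1 states 89%. The method matches 29 of the 30 cells within 2 points. The exception (background 2%, RR 1.5: stated 99, computed 94) does not bear on this point.

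**3. Use in the unexposed cohort.** Let a share f of unexposed time be on another agent with the same RR. Then observed RR = RR / (1 + f(RR − 1)). For RR 2 and f = 10%, 2/1.10 = 1.82; for f = 20%, 2/1.20 = 1.67. The documents give no f, so a range is shown. Each cell is observed RR / power, from the same test with the unexposed rate raised.

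| Background, true RR | f = 0 | 5% | 10% | 20% | 30% |
|---|---|---|---|---|---|
| 0.5%, RR 2 | 2.00 / 89.6% | 1.90 / 85.7% | 1.82 / 81.0% | 1.67 / 69.5% | 1.54 / 56.2% |
| 0.2%, RR 3 | 3.00 / 94.5% | 2.73 / 91.4% | 2.50 / 87.3% | 2.14 / 76.1% | 1.88 / 61.9% |
| 0.1%, RR 4 | 4.00 / 92.6% | 3.48 / 88.5% | 3.08 / 83.3% | 2.50 / 70.2% | 2.11 / 55.4% |

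In the first row, power drops below the 80% of section 11 somewhere between f = 10% and 20%. At background 1% and RR 2 it is still 94.2% at 20%.

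**4. Use in the exposed cohort.** Let g be the share of exposed time on another agent.

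- If joint effects multiply, observed RR = RR(1 + g(RR − 1)) / (1 + f(RR − 1)). For RR 2: g 20%, f 0 gives 2 × 1.20 = 2.40; 20% in both gives 2.00; g 30%, f 10% gives 2 × 1.30/1.10 = 2.36; g 10%, f 30% gives 2 × 1.10/1.30 = 1.69.
- If a second agent adds nothing to the first, concurrent use in the exposed cohort leaves the ratio unmoved: 20% in both gives 2/1.20 = 1.67.
- After a switch, assume 40% of exposed follow-up is off romiplostim and RR is 3. With no other agent the ratio is 0.6 × 3 + 0.4 × 1 = 2.20. With half of the off-drug time on a same-effect agent it is 0.6 × 3 + 0.4 × (0.5 × 3 + 0.5 × 1) = 2.60. The other agent has raised it.
- If romiplostim has no effect and the other agent has RR 3, g 30% and f 10% give 1.60/1.20 = 1.33; g 10% and f 20% give 1.20/1.40 = 0.86. Either error is possible with a null drug.

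**The case against.** The best defence is that the protocol does not overlook these agents. It extracts the data, lists the variable, plans multiple regression, and promises narratives with treatment history for every marrow fibrosis case. Sections 7.1 and 7.2 confine treatment time to romiplostim dosing plus 10 days, so post-switch events can be told apart from on-treatment events. The primary objective is a rate in recipients, every contrast is exploratory, and section 13 warns that comparability may fail. Covariate detail may properly sit in the SAP. All of that stands, and it limits the weight of the point. It does not change how the protocol itself defines eligibility, exposure and time at risk, from which the crude rates follow.

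Stronger readings go too far:

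- A reader might infer that use in both cohorts pulls the comparison toward no difference. Only unexposed-side use does; step 4 shows the ratio unchanged or raised by exposed-side use.
- A reader might infer that the trial exclusion removes romiplostim patients who join such a trial after the index date. The sentence is undated, so this is one reading, and it sits uneasily with section 9, which follows all patients and has no removal procedure.
- A reader might infer that effects of RR 2 to 4 become undetectable. The share of use and an equal class effect are assumptions, and step 3 shows power holding at higher background rates.
- A class effect on thrombosis is not stated in the protocol. The marrow outcomes are where its own text supports the concern.

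**Conclusion.** The point holds as a gap in definitions. Prescribed use of another TPO receptor agonist is counted in whichever romiplostim-defined cohort the patient is in, and none of the planned handling separates the crude rates. On the unexposed side the size could matter: RR 2 becomes 1.82 at 10% use and 1.67 at 20%, with power at background 0.5% falling from 89.6% to 81.0% and 69.5%. These figures assume the share of use, an equal effect across the class, and two-sided alpha 0.05. The documents do not say how much such use there is; if it is negligible, so is the bias. On the exposed side the problem is attribution, and the net direction of the rate ratio cannot be known from the documents. Because comparisons are exploratory, this is a change that should be made and not a flaw that defeats the study.

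**What to change.** In sections 6.1 and 7.3, treat use of another TPO receptor agonist as a time-varying exposure state from its first recorded use. Report the primary marrow and thrombotic incidence rates for four categories: no agent; other agent only; romiplostim only; romiplostim plus, or followed by, another agent. Show them beside the as-written cohort rates, not in place of them. In section 12.4, make time-varying adjustment for other agents firm in any model that is fitted. In section 3.4.2, state that the trial exclusion applies at or before the index date, and that later trial entry splits or censors person-time at enrolment instead of removing the patient.

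The cost is protocol wording and extra table columns, since section 3.1 already extracts the data. There are real downsides: fewer patient-years per category, switching that may be informative, and a no-agent comparator that may have milder disease, which could worsen the severity confounding named in section 8. For that reason the two sets of rates should be interpreted together.

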All cases with BM fibrosis will be described in detailed narratives with respect to underlying disease, comorbidities, treatment history, medications, any possible risk factors, and demographic characteristics. This descriptive data will be summarized in the clinical study report.

All romiplostim-exposed patients who develop hematologic malignancies will be described in detailed narratives with respect to underlying disease, comorbidities, treatment history, medications, any possible risk factors, and demographic characteristics. This descriptive data will be summarized in the clinical study report.

Special analyses will be conducted for chronic ITP patients with renal impairment medical conditions at the time romiplostim therapy is initiated. The analysis will include multivariate analysis justifying for renal comorbidities and/or medical history, as well as stratified analysis based on renal impairment status at romiplostim therapy initiated. Other outcomes listed in this study proposal will also be described within each predefined stratum.

Analysis for romiplostim off-label users is descriptive in nature for the purpose of hypothesis generation. The analyses will describe the off-label study population in different study time periods.

Since comparative analyses will be inherently challenging to interpret, any comparative analyses will be considered as exploratory for signal detection and for the purpose of hypothesis generation. The study will also compare the incidence rates from the romiplostim exposed cohort to that from other potential sources where sufficient data may be present:

- Amgen Study 20080092 (Nplate™ Patient Safety Registry – Canada version)
- Amgen Study 20080045 (Nplate™ Patient Safety Registry – US version)
- Amgen Study 20070796 (Determination of Frequency Rates of Bone Marrow Fibrosis and Thrombotic/Thromboembolic Events in Patients with Chronic Immune (Idiopathic) Thrombocytopenic Purpura in Denmark)
- Administrative databases such as SEER, Ingenix, and GPRD, if appropriate data are available at time of analysis
- Published data on the frequency of predefined risks, such as [Mufti et al \(2007\)](#) and [Aledort et al \(2004\)](#)
- Data available from Amgen's ongoing romiplostim clinical program

The safety data will be assessed annually and the findings will be reported in appropriate context to the regulatory agency via the PSUR, and will include the following:

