6.2 Outcomes

There are many outcomes in the NCPRR. They are:

Primary Outcome Endpoints:

- Incidence of increased BM reticulin and/or BM fibrosis with associated clinical signs⁴, confirmed by findings in BM biopsies among adult chronic ITP patients
- Incidence of reticulin and collagen BM fibrosis (reticulin fibrosis and collagen fibrosis: SNOMED codes: M49000, M49001, M49020, M99611) with associated clinical signs, confirmed by findings in a BM biopsy among adults chronic ITP patients

Secondary Endpoints:

Clinical Endpoints:

- Average platelet counts prior to, during, immediately after treatment cessation, and following romiplostim therapy (study periods are defined in [Section 7.1](#))
- Incidence of thrombocytosis (laboratory confirmation of a platelet count $> 450 \times 10^9/L$) with/without adverse events among adult chronic ITP patients
- Incidence of thrombotic/thromboembolic events (ICD-10: 180, 126)
- Incidence of hematological malignancies (focused on AML and MDS)
- Incidence of clinically significant bleeding and/or receipt of rescue ITP medications for each predefined romiplostim treatment period ([Section 7.1](#))
- Incidence of concurrent leukocytosis and anemia (measured by laboratory test results taken within 4 weeks of each other)
- Description of platelet counts and dose adjustment in mcg/kg of romiplostim in patients with cITP according to dose adjustment rules specified in the European SPC

⁴ Clinical signs: any of the following: splenomegaly, hepatomegaly, leukocytosis, and cytopenia.

BM Endpoints:

- Prevalence of reticulin and collagen fiber content in the first BM biopsies of adult chronic ITP patients prior to romiplostim therapy by splenectomy status
- Incidence of collagen fibrosis with associated clinical signs confirmed by findings in BM biopsies among adult chronic ITP patients
- Incidence of PMF (primary myelofibrosis) (ICD-10: c94.5) according to the WHO diagnostic criteria in adult chronic ITP patients who have BM data prior to and/or post romiplostim therapy
- Overall and specific incidence of BM fibrosis, including reticulin and collagen fiber content formation, and PMF among adult chronic ITP patients with BM data prior to and/or post romiplostim therapy
- Association between the aforementioned primary and secondary clinical outcomes and BM abnormal findings

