Appendix 2. Conditions Associated with Thrombocytopenia Other Than cITP

Diseases and Condition	ICD-10 Codes
Hereditary syndromes and Immunodeficiency:	
Alport syndrome	Q87.8
Fanconi anemia	D61.0B
May Hegglin anomaly	D72.0 (genetic abnormalities of leukocytes)
CVI (hypogammaglobulinemia)	D80.0, D80.1 (hereditary and nonfamilial hypogammaglobulinemia)
IgA deficiency	D80.2
IgG subclass 2 deficiency	D80.3
Low C4 counts	D84.1 (defects in the complement system)
Systemic "Global" autoimmunity:	
Evans syndrome and autoimmune hemolytic anemia	D69.3 & D59.0/D59.1
Systemic lupus erythematosus (SLE)	M32
Infections:	
HIV/AIDS	B20-B24
Hepatitis C	B17.1, B18.2
Lymphoproliferative disorders Malignant:	
Solid tumor	C00-C80
Hematological malignancies	C81-C96
Lymphoproliferative disorders non-Malignant:	
Autoimmune lymphoproliferative syndrome type I (ALPS) (or Canale-Smith syndrome)	D36.0 (benign neoplasms of lymph nodes)
Liver disorders:	
Diseases of liver	K70-K77
Bone marrow disorders	
Agranulocytosis	D70
Aplasia pure red cell	D60
Aplastic anaemia,pancytopenia	D61.0, D61.1, D61.2, D61.3, D61.9
Bone marrow transplant rejection	T86.0
Bone marrow tumour cell infiltration	Z94.8
Myelodysplastic syndrome	D46
Myelofibrosis	C94.5
Myeloproliferative disorder	D47.1
Other transplants, incl. bone marrow	Z94.8
Other disorders involving platelets	
Allergic purpura	D69.0
Qualitative platelet defects	D69.1
Secondary thrombocytopenia	D69.5
Antiphospholipid syndrome	D68.8 (coagulation defects)
Disseminated intravascular coagulation	D65
Hemolytic-uremic syndrome	D59.3
Thrombocytopenia neonatal	P61.0
Thrombotic thrombocytopenic purpura	M31.1
von Willebrand's disease	D68.0
Wiskott-Aldrich syndrome	D82.0

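### The Appendix 2 exclusion window overlaps counted follow-up, so early AML, MDS and myelofibrosis cases drop out of the incidence rates meant to capture them

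*Protocol*

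**What the plan says.** Section 3.4.2 removes from the chronic ITP cohorts any patient with an Appendix 2 condition "at any time prior to or within 6 months after the qualifying diagnosis for chronic ITP". Its examples include "malignancy, lymphoproliferative disorders, and myelodysplastic syndrome". The synopsis carries the same rule.

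Appendix 2 lists haematological malignancies (C81-C96), "Myelodysplastic syndrome" (D46) and "Myelofibrosis" (C94.5).

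Section 6.2 makes AML/MDS a secondary endpoint and adds "Incidence of PMF (primary myelofibrosis) (ICD-10: c94.5) according to the WHO diagnostic criteria in adult chronic ITP patients". The PMF endpoint and the Appendix 2 myelofibrosis entry share one code.

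On timing:
- Section 4.1 sets the exposed Index Date at first romiplostim.
- For unexposed patients diagnosed on or after 01 April 2009 the Index Date is the date of diagnosis. For those diagnosed earlier it is 01 April 2009.
- Section 7.3 runs time at risk from the Index Date, or from first romiplostim exposure, with no lag.
- Section 3.4.1 asks exposed patients for 6 months of prior medical information. It sets no minimum interval between the chronic ITP diagnosis and the first dose.

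Section 3.4.1 also defines off-label users as "any patient who received romiplostim therapy without an adult chronic ITP diagnosis". The synopsis (Statistical Considerations) promises: "All romiplostim-exposed patients who develop hematologic malignancies will be described in detailed narratives".

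**The concern.** Eligibility should be settled by what is known when follow-up begins. Here it can depend on something that happens afterwards. A patient already contributing time at risk who is diagnosed with MDS, AML or myelofibrosis inside the window is removed from the cohort, and the event goes too. Those who stay are free of these outcomes in that period by construction, yet their time is counted.

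The endpoints concerned are rare. Section 12.4 expects too few AML and MDS cases for meaningful statistical comparison and relies on case descriptions, so a single lost case matters. Section 2.3 names possible stimulation of existing haematopoietic malignancy or MDS, in patients whose thrombocytopenia is not due to ITP, as a potential risk. Cases that surface soon after diagnosis bear directly on that question.

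The loss need not be equal. On the most direct reading, every incident unexposed patient spends the window in follow-up, whereas exposed patients spend it on romiplostim only if they start early.

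An excluded romiplostim user also has no clear place. The patient does have a chronic ITP diagnosis, so the 3.4.1 off-label definition does not strictly fit. But 3.1 gives MDS as an example of off-label use, so an outcome could be recorded as an indication.

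**Working it through.** **Plan's own counts (section 3.5).**
- Prevalent: 570 × 13 = 7410; × 0.20 = 1482; × 0.95 = 1408; × 0.25 = 352 exposed.
- Incident: 5700 × 0.20 = 1140; × 0.95 = 1083; × 0.25 = 271 exposed.
- Exposed total: 352 + 271 = 623, as stated.
- Incident unexposed: 1083 − 271 = 812.
- Unexposed total: 1408 + 1083 − 623 = 1868, against 1860 stated, which is close enough.

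The 4,234 and 12,700 patient-years are taken as stated; they cannot be derived from the inputs given.

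**Who is affected.** Incident patients mainly. Most prevalent patients passed the 6-month point before their Index Date. The exception is a small group who qualified from about October 2008, whose window runs past 01 April 2009.

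**Unexposed time inside the window.** The protocol does not define the qualifying diagnosis (3.4.2) against the date of diagnosis (4.1), so there are three readings:

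| Reading | Time outcome-free by construction | Patient-years | Share of 12,700 |
|---|---|---|---|
| Index Date is the qualifying date | 0.5 year | 812 × 0.5 = 406 | 3.2% |
| Index Date is the first ITP code; chronicity qualifies 6 months later | 1.0 year | 812 × 1.0 = 812 | 6.4% |
| Qualifying diagnosis is the first ITP code; follow-up starts when chronicity is met | none | near 0 | near 0% |

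These figures leave out the pre-romiplostim time of patients exposed later, which 3.1 also counts as unexposed.

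**Exposed time inside the window.** Ceiling: all 271 incident users start romiplostim on the qualifying date. 271 × 0.5 = 135.5 patient-years; 135.5 / 4,234 = 3.2%. The protocol does not say how many start that early.

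**Expected lost events.** Section 11 says background rates are unknown, so 0.1% to 0.5% per year is assumed.
- Exposed, at the ceiling: 135.5 × 0.001 = 0.14; 135.5 × 0.005 = 0.68.
- Unexposed, on 406 patient-years: 406 × 0.001 = 0.41; 406 × 0.005 = 2.03.

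**If early hazard is higher.** This is plausible, since haematological disease may be recognised soon after an ITP label, but the multiple is assumed. Let the hazard in the window be h times the later hazard, with 12,700 − 406 = 12,294 patient-years outside it.
- Share of unexposed events lost = 406h / (12,294 + 406h).
- If no exposed events are lost, a true ratio of overall rates of 1.00 appears as (12,294 + 406h) / 12,294.

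| h | Share lost | Apparent ratio |
|---|---|---|
| 1 | 3.2% | 1.03 |
| 3 | 9.0% | 1.10 |
| 5 | 14.2% | 1.17 |
| 10 | 24.8% | 1.33 |

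In this scenario the error runs against romiplostim. If early starters also lose events, the exposed rate falls too.

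**The case against.** The rule has a sound purpose. Sections 3.1 and 5.1 note that ITP is a diagnosis of exclusion and that secondary causes can be hard to recognise. The Amendment 3 rationale shows that running the window 6 months past the qualifying diagnosis was deliberate. MDS or leukaemia found within months of an ITP label may have caused the thrombocytopenia from the start. This stands, and it is a reason to keep the exclusion. It does not justify counting the survivors' in-window time at risk for the same outcomes.

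The effect is also limited. Later events, over up to 11 years, still count. The endpoints are secondary, the study is descriptive, and comparisons are labelled exploratory. All of that stands.

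A reader might infer that long-latency malignancy rates are seriously compromised. The documents do not support this: long-latency events are the least likely to fall in a 6-month window. Nor do they support an inference that the primary endpoint is compromised, because biopsy-confirmed reticulin or fibrosis is touched only when the case also carries an Appendix 2 code.

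A reader might also infer that case narratives disappear. The exclusion is from the chronic ITP cohorts, not from the registry. The synopsis promises narratives for all exposed patients who develop haematological malignancy, and 12.2 allows for narratives of secondary thrombocytopenia. Narratives do not, however, put a case back into a rate.

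**Conclusion.** The point holds. For incident unexposed patients, and for patients who start romiplostim inside the window, 3.4.2 conditions cohort membership on being free of AML, MDS, other haematological malignancy and C94.5 during time that 7.3 counts as at risk. These rates are biased down, possibly unequally between cohorts.

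The size is modest. About 406 unexposed patient-years (3.2%) are affected if the Index Date is the qualifying date. It is tempting to quote 812 (6.4%), but that needs the Index Date to be the first ITP code with qualification 6 months later. The near-zero reading cannot be excluded either, although 3.4.2 ties the qualifying diagnosis to chronic ITP and refers separately to the first ITP diagnosis code, which tells against it. Even on that reading, early romiplostim starters remain affected.

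On the exposed side, 135 patient-years and 0.1 to 0.7 lost events are ceilings: they assume that all 271 incident users start on the qualifying date, at an assumed 0.1-0.5% per year. Most prevalent patients are unaffected. This is worth correcting because the outcomes are rare and the correction is cheap; it does not undermine the registry.

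**What to change.** - Keep the exclusion window. Define the qualifying diagnosis in 3.4.2 against the date of diagnosis in 4.1.
- For AML, MDS, other haematological malignancies and PMF, start time at risk in both cohorts at the later of the Index Date and the close of the window, 6 months after the qualifying diagnosis.
- List and narrate every in-window case by romiplostim exposure at the time of the event. State that such cases are not reclassified as off-label use.
- Add a sensitivity analysis that counts in-window cases after the Index Date, with their person-time.

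Limiting the exclusion to diagnoses before the Index Date looks simpler but should be avoided. The Index Date is first dose in one cohort and, for incident patients, date of diagnosis in the other. A prevalent exposed patient who developed a solid tumour or liver disease in the years between ITP diagnosis and romiplostim would be newly excluded, while an unexposed patient with the same history could stay. Outcomes in pre-romiplostim time, which 3.1 counts as unexposed, would also delete the patient.

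Cost: wording in 3.4.2, 4.1 and 7.3, one listing, one sensitivity analysis, and a small loss of early person-time from the main rates of these outcomes.
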